### **14.3.6 Unexpected adverse event**

An adverse event or suspected adverse reaction is considered “unexpected” when its nature, severity or frequency is not consistent with the information that is provided with the information in the protocol.

## **14.4 Collecting, recording and managing adverse events**

### **14.4.1 Identifying adverse events**

Any adverse event that occurs from the moment the subject has signed the consent form will be recorded and is reportable. Collection time for AEs and SAEs will begin after the screening visit when the consent form is signed and will continue until the end of the treatment.

Adverse events may be discovered through any of these methods:

- Observing the participant
- Questioning the participant, with standardized questions/procedures.
- Receiving an unsolicited complaint from the participant.
- An abnormal value or result from a clinical or laboratory evaluation can also indicate an adverse event when determined to be clinically significant by the Principal Investigator.

### **14.4.2 Recording AEs**

Throughout the study all identified adverse events (serious and non-serious) will be recorded on all appropriate source document and adverse event case report forms regardless of their severity or relation to the study. A complete description of all adverse events will include event description, time of onset, investigator assessment of severity, relationship to study agent or procedures, time of resolution/stabilization of the event, expectedness, determination of whether the AE qualifies as a SAE, and action taken. A change in the severity of the AE will also be documented. Assessment of severity and relationship will be documented on the source documents or the on the CRF.

#### 14.4.3 Recording SAEs

Serious adverse events will be recorded on the serious adverse event case report form and will include a narrative of the event signed and dated by the Principal Investigator.

Adverse event reporting timeline

- Within **24 hours** (of learning of the event), investigators must report any reportable Serious Adverse Event (SAE) that:
  - Is considered life-threatening/disabling or results in death of subject

-OR-

- Investigators must report all other reportable SAEs within **5 working days** (of learning of the event).
- All other (suspected) reportable AEs must be reported to the DSMB and the IRB within **20 working days** of the notification of the event or of the investigators becoming aware of the event.

#### 14.5 Managing adverse events

The study investigator must apply his or her clinical judgment as to whether an AE is of sufficient severity to require that the participant immediately be removed from further receiving the study agent under the protocol. The investigator must institute any necessary medical therapy to protect a participant from any immediate dangers.

An adverse event will be followed until any of the following takes place: a) it is resolved, b) participant is stable, c) a minimum of 30 days after participant is terminated from the study and the Principal Investigator determines that follow-up is no longer needed.

If an abnormal value or result from a clinical or laboratory evaluation is determined to be an AE, then the evaluation that produced the value or result can be repeated until the value or result returns to normal, or the result can be explained, or the usual standard of care does not require further follow-up, and the participant's safety is not at risk.

Non-serious expected adverse events will be submitted to the DSMB in a timely fashion. The events will be presented in tabular form and given to the DSMB on a bi-annual basis. Study investigators are also required to fulfill all reporting requirements of their local institutions.

## 14.6 Grading and Attribution

### 14.6.1 Grading Criteria

In addition to determining whether an adverse event fulfills criteria for a serious adverse event or not, the severity of adverse events experienced by study participants will be graded according to the criteria set forth in the National Cancer Institute's Common Terminology Criteria for Adverse Events Version V4.0. This document (referred to herein as the NCI-CTCAE manual) provides a common language to describe levels of severity, to analyze and interpret data, and to articulate the clinical significance of all adverse events. All adverse events whether or not listed in the NCI-CTCAE will be graded on a scale from 1 to 5 according to the following standards in the NCI-CTCAE manual (A semi-colon indicates 'or' within the description of the grade):

**Grade 1** = Mild; asymptomatic or mild symptoms; clinical or diagnostic observations only; intervention not indicated.

**Grade 2** = Moderate; minimal, local or noninvasive intervention indicated; limiting age-appropriate instrumental ADLs (preparing meals, shopping for groceries or clothes, using the telephone, managing money, etc).

**Grade 3** = Severe or medically significant but not immediately life-threatening; hospitalization or prolongation of hospitalization indicated; disabling; limiting self care ADLs (bathing, dressing and undressing, feeding self, using the toilet, taking medications, and not bedridden).

**Grade 4** = Life-threatening consequences; or urgent intervention indicated.

**Grade 5** = Death related to AE.

## 14.7 Definition of Attribution

The attribution, of an adverse event to the study will be determined by the Principal Investigator or designated physician co/sub-investigator. The Principal Investigator or designee will record the determination of attribution on the appropriate adverse event or serious adverse event form. The attribution of an adverse event to the investigational drug or to a study procedure will be determined using the descriptors in the following table. For the purpose of this study, in addition to all study medications, the following procedures will be considered when determining attribution:

## Attribution of adverse events

Code	Descriptor	Definition (guidelines)
UNRELATED CATEGORY		
1	Unrelated	The adverse event is clearly not related to study. The event is completely related to an etiology other than the study product or study intervention (the alternative etiology must be documented in the study subject's medical record)
2	Unlikely	The adverse event is doubtfully related to study and likely to be related to factors other than study product or study intervention.
RELATED CATEGORIES		
3	Possible	The adverse event may be related to study. There is an association between the event and the administration of study product and there is a plausible mechanism for the event to be related to the study product; there may be also an alternative etiology, such as characteristics of the subject's clinical status and/or underlying disease
4	Probable	The adverse event is likely related to study. There is (1) an association between the event and the administration of study product or study intervention, (2) a plausible mechanism for the event to be related to the study product, and (3) the event could not be reasonably explained by known characteristics of the subject's clinical status and or an alternative etiology is not apparent
5	Definite	The adverse event is clearly related to study. There is (1) an association between the event and the administration of the study product or study intervention, (2) a plausible mechanism for the event to be related to the related to the study product, and (3) causes other than the study product have been ruled out and/or the event re-appeared on re-exposure to the study product

(For additional information and a printable version of the NCI-CTCAE manual, consult the NCI-CTCAE website: <http://ctep.cancer.gov/reporting/ctc.html>) will be consulted.)

In a clinical trial, the study product\intervention will always be suspect when attributing an AE and the “unrelated” attribution will be used only when there is an undisputable or likely alternative explanation for the AE.

## **14.8 SAE Reporting Criteria and Procedures**

The Principal Investigator will be notified by the study staff as soon as a study staff member becomes aware of the SAE. In the absence of the Principal Investigator, a physician sub-investigator will be notified.

The Principal Investigator determines causality (definitely not related, probably not related, possibly related, probably related, definitely related) of the adverse event. The DSMB Chair may request further information if necessary and possibly request changes to the protocol or consent form as a consequence of the adverse event. A back-up notification system will be instituted so that any delays in review by the Chair beyond a specified period of time are forwarded to a secondary reviewer.

### **14.8.1 Unexpected, non-serious adverse events**

An unexpected, non-serious adverse event that is of Grade 3 severity or higher and study related will be recorded and reported under the serious adverse event reporting procedure (i.e. within 24 hours).

### **14.8.2 Notifying the FDA**

The IND sponsor (The PI) is responsible for FDA safety submissions as follows: The IND Sponsor for this study will handle all regulatory communications with the Food and Drug Administration and will be responsible to update the IND to include this trial, file all regulatory related issues including any MEDWATCH reports which will be reviewed and approved by the PI and Steering Committee. The IND sponsor will be responsible for submission of yearly reports and final report for this study. All DSMB recommendations will be communicated to the IND sponsor in a timely fashion.

The following process for reporting a serious adverse event ensures compliance with the ICH guidelines, 21CFR §312.32.

- Expedited safety report to the FDA applies if the adverse event is classified as one of the following:
  - Serious and unexpected suspected adverse reaction (SUSAR) (Sections 14.3.4, 14.3.6, and 14.7) (i.e. serious, unexpected, and related)

Or
  - Aggregate analysis of adverse events that suggest a causal relationship to the study medications

Or
  - Any findings from clinical, epidemiological, pooled analysis of data pooled across multiple studies, published or unpublished scientific papers or any findings from animal or in vitro testing that would result in a safety-related change in the protocol, informed consent, investigator

brochure or other aspects of the overall conduct of the trial will be reported.

Expedited Safety Reports must be reported by the IND Sponsor to the FDA within 15 calendar days; fatal or immediately life-threatening serious, unexpected, suspected adverse reactions must be reported within 7 calendar days. SAEs that do not strictly fit the above criteria may be reported to the FDA in an expedited manner if the IND Sponsor chose to do so. Each 7-day report must be followed up by a 15-day report.

The following types of SAEs will be reported in the IND Annual Report:

- Serious, expected, suspected adverse reactions
- Serious but not a suspected adverse reaction

For standard reporting, the IND Sponsor or designee will file the IND Annual Report. All adverse events (not just those requiring 24 hour reporting) will be reported in the Annual IND Report.

#### **14.8.3 Notifying the Data and Safety Monitoring Board**

The PI will submit all safety reports on an ongoing basis to the DSMB. Individual or clusters of SAEs may be reported expeditiously to the DSMB upon determination.

#### **14.8.4 Notifying the Institutional Review Board**

The Principal Investigator will ensure the timely dissemination of SAE information, including expedited reports, to the IRB in accordance with IRB regulations and guidelines.

#### **14.9 Reporting Pregnancy**

A research subject will be terminated from the study due to pregnancy. The principal investigator will be informed immediately of any pregnancy and will report all pregnancies within 24 hours of becoming aware of the event to DSMB utilizing the SAE report form. This report is for tracking purposes only. All pregnancies that are identified during the study will be followed to conclusion and the outcome of each will be reported. The site principal investigator will discuss with the participant and/or the treating physician the known possible risks of the investigational product(s) on the fetus. Monitoring of the participant will continue until the conclusion of the pregnancy, and a follow-up SAE report form detailing the outcome of the pregnancy will be submitted to the DSMB.

#### **14.10 Non-serious adverse events (NSAEs) reporting**

##### **14.10.1 Notifying the data and safety monitoring board**

The DSMB will be notified of non-serious adverse events during their regularly scheduled meetings. The events will be presented to the Board in tabular format.

#### **14.10.2 Notifying the FDA**

The IND sponsor (the Study Chair) will file all adverse events per 21 CFR 312.32, whether expedited or part of the IND Annual Report. The IND sponsor will be responsible for compiling the IND Annual Report.

#### **14.10.3 Notifying the Institutional Review Board**

The Principal Investigator will ensure the timely dissemination of AE information to the IRB in accordance with applicable regulations and guidelines.

#### **14.10.4 Unanticipated Problems**

The Office for Human Research Protections (OHRP) considers unanticipated problems involving risks to subjects or others to include, in general, any incident, experience, or outcome that meets **all** of the following criteria:

Unexpected in terms of nature, severity, or frequency given (a) the research procedures that are described in the protocol-related documents, such as the IRB-approved research protocol and informed consent document; and (b) the characteristics of the subject population being studied;

Related or possibly related to participation in the research (“possibly related” means there is a reasonable possibility that the incident, experience, or outcome may have been caused by the procedures involved in the research); and

Suggests that the research places subjects or others at a greater risk of harm (including physical, psychological, economic, or social harm) than was previously known or recognized.

Incidents or events that meet the OHRP criteria for unanticipated problems will be reported to the DSMB and IRB, in the following time frames:

1. Unanticipated problems that are serious adverse events should be reported to the IRB within 1 week of the investigator becoming aware of the event.
2. Any other unanticipated problem should be reported to the IRB according to the IRB’s reporting policies.

#### **14.11 Data Management**

All study data will be collected via systems created by using RedCap (an online data management software) and will comply with all applicable guidelines regarding patient confidentiality and data integrity.

#### **14.11.1 Registration**

Registration of participants on this protocol will employ an interactive data system in which the clinical site (University of Cincinnati) will attest to the participant’s eligibility as per protocol criteria and obtain appropriate informed consent. IRB approval for the protocol must be obtained before accrual can occur from the clinical site.

Each participant enrolled will be assigned a local identifier by the enrollment site. This

number can be a combination of the site identifier (location code) and a serial accession number. Only the registering site will have access to the linkage between this number and the personal identifier of the subject.

#### **14.11.2 Data Entry**

Data collection for this study will be accomplished with a combination of paper as well as online electronic case report forms. Using encrypted communication links, on-line forms will be developed that contain the requisite data fields.

#### **14.11.3 Data Quality and Monitoring Measures**

As much as possible data quality is assessed at the data entry point using intelligent on-line data entry via visual basic designed screen forms. Data element constraints, whether independent range and/or format limitations or ‘relative’ referential integrity limitations, can be enforced by all methods employed for data input. QA reports assess data quality post-data entry. As we note, data quality begins with the design of the data collection forms and procedures and incorporates reasonable checks to minimize transcription and omission errors. Of the more important quality assurance measures are the internal validity checks for reasonableness and consistency.

The DSMB will review data quality on an ongoing basis. A risk-based monitoring plan will be developed to support the study. The purposes of study monitoring are to ensure the safety and welfare of study participants and to confirm the accuracy of study data.

An onsite monitoring visit will occur once during the conduct of the trial, with the option of making a second visit if determined by Principal Investigator to be needed, to address enrollment, or protocol deviation issues. The Monitoring Plan will detail the frequency and level of intensity of on-site monitoring visits. In general, the study will be monitored for all participants at a level of 100% of study data gathered for inclusion and exclusion criteria, informed consent procedures, adverse events and unanticipated problems. The study monitor(s) will collaborate with the Principal Investigator to conduct remedial site training to ensure compliance with GCP and all regulations.

During scheduled interim remote monitoring visits, the clinical monitors will verify that the protocol is being followed and that data are being collected according to protocol requirements. The clinical monitor(s) will review the Study Regulatory File to determine that all required documentation is being collected and that the IRB approval for the site is current. The monitor will then verify that each participant has signed the correct version of the informed consent document, and that this document is filed in the participant’s source documents. At each visit, the monitor will perform an audit of the source documents in the subject’s binder by checking them against the database. Adverse event documentation will be checked for completeness and accuracy. At the study closeout, the monitor(s) will confirm that all data have been reviewed, all source documents have been verified, and all required documents are present in the Study Regulatory File.

Protocol deviations and unanticipated problems will be reviewed by the Principal Investigator, and the regulatory and monitoring staff to determine the need for corrective and preventative action (CAPA). In the event that corrective and/or preventative action is

warranted, a root cause analysis will be performed and a CAPA will be completed as per institutional policy. The Principal Investigator is responsible for communicating the CAPA plan to appropriate staff (i.e. Site Investigator, study team) and obtaining appropriate signatures to address the issues at hand. The Principal Investigator will work with regulatory and monitoring staff to insure that the CAPA is followed and is effective in resolving the issue(s). Protocol deviations and unanticipated problems will be reported to the IRB as per institutional policy.

The table below describes the variables to be reviewed during monitoring visits.

Variable	% of Records Reviewed
Informed consents	100%
Eligibility criteria for all screened subjects	100%
Adverse events	100%
Protocol adherence	20% of active subjects
Verification of REDCap with source documents	20% of active subjects
Central study files-inclusion of all applicable documents	100%
Protocol deviations/violations	100%

## 14.12 Protocol Deviations

The practices below are consistent with Good Clinical Practice (GCP ICH E6) Sections:

- Compliance with Protocol, sections 4.5.1, 4.5.2, and 4.5.3
- Quality Assurance and Quality Control, section 5.1.1
- Noncompliance sections 5.20.1, and 5.20.2

### 14.12.1 Protocol deviation Definition

**14.12.1.1 Protocol Deviation** - Any change, divergence, or departure from the study design or procedures of a research protocol that affects the subject's rights, safety, or well-being and/or the completeness, accuracy and reliability of the study data constitutes a protocol violation. Changes or alterations in the conduct of the trial which do not have a major impact on the subject's rights, safety or well-being, or the completeness, accuracy and reliability of the study data are considered non-major protocol deviations. Site Principal Investigator is responsible for reporting protocol deviations to the IRB using the standard reporting form. As a result of deviations, corrective actions are to be developed

by the site and implemented promptly.

**14.12.1.2 Major Protocol Deviation (Protocol Violation)** - A protocol violation is a deviation from the IRB approved protocol that may affect the subject's rights, safety, or well-being and/or the completeness, accuracy and reliability of the study data.

If the deviation meets any of the following criteria, it is considered a major protocol deviation. However, the lists of deviation examples that follow are not exhaustive.

- The deviation has harmed or posed a significant or substantive risk of harm to the research subject.

Examples:

1. A research subject received the wrong treatment or incorrect dose.
2. A research subject met withdrawal criteria during the study but was not withdrawn
3. A research subject received an excluded concomitant medication.

- The deviation compromises the scientific integrity of the data collected for the study.

Examples:

1. A research subject was enrolled but does not meet the protocol's eligibility criteria.
2. Changing the protocol without prior IRB approval, except for modification to ensure the safety of study participants.
3. Inadvertent loss of samples or data.

- The deviation is a willful or knowing breach of human subject protection regulations, policies, or procedures on the part of the investigator(s).

Examples:

1. Working under an expired professional license or certification.
2. Failure to follow federal and/or local regulations.
3. Repeated minor deviations.

- The deviation is inconsistent with the NIH Human Research Protection Program's research, medical, and ethical principles.

Examples:

1. A breach of confidentiality.
2. Inadequate or improper informed consent procedure.

**14.12.1.3 Non-Major Protocol Deviation** - A non-major protocol deviation is any change, divergence, or departure from the study design or procedures of a research protocol that has not been approved by the IRB and which DOES NOT have a major impact on the subject's rights, safety or well-being, or the completeness, accuracy and reliability of the study data.

#### **14.12.2 Reporting Protocol Deviations**

Deviations from the protocol are not allowed. It is the responsibility of the study site to use continuous vigilance to identify and report any protocol deviations. Upon determination that a protocol deviation has occurred, the study staff will a) notify the Principal Investigator, b) notify Project Manager and c) complete the Protocol Deviation form. The Principal Investigator will complete and sign the Protocol Deviation form and submit it to the IRB, per IRB regulations. Major protocol deviations will be reported to the DSMB at the regular DSMB reporting interval. The IND sponsor (PI) will also be responsible for notifying the FDA.

## 15. Statistical considerations:

*Sample size determination:* As mentioned previously, the mean serum VEGF-D level prior to treatment was approximately 2,000pg/ml in both the MILES trial (12) as well as the everolimus trial (18). In both studies, treatment with mTOR inhibitors resulted in an almost 50% reduction in the serum VEGF-D levels (12, 18). Since patients in our study will be on sirolimus prior to enrolment, we estimate that the starting serum VEGF-D level in our study will be approximately 1,000pg/ml. The largest change between serial VEGF-D levels in the placebo group of MILES was 42%. Thus, VEGF-D responders in MILES trial were conservatively defined as patients in whom serum VEGF-D decreased to a value greater than 42% from its baseline (16). Accordingly, we made our power calculations based on the ability to show a greater than or equal to 42% change in serum VEGF-D levels. Assuming the correlation between the baseline and subsequent VEGF-D levels is 0.7, a sample size of 20 subjects will provide 80% power to detect a mean VEGF-D difference from baseline to post-treatment of 420pg/ml or higher with the level of significant of 0.05 and a standard deviation of 800 for the difference. Allowing for a 20% dropout rate, we expect to recruit 25 patients for our study. Sample size calculations were done using SAS version 9.4.

*Data Analysis:* The analysis will be based on an intention to treat design. All subjects that receive study drug will be included in the safety and efficacy analysis set. The primary analysis will occur after the last enrolled participant has completed the 24-week visit. All analyses will be performed using SAS version 9.4. A p-value less than 0.05 will be considered as statistically significant.

**Specific Aim #1:** To determine if combined resveratrol and sirolimus leads to reduction in serum VEGF-D compared to VEGF-D reduction on sirolimus alone. Paired t-test will be performed to detect the difference of serum VEGF-D after 24 weeks of treatment with the serum VEGF-D prior to enrolment. The response variable VEGF-D will be measured repeatedly, at baseline and at weeks 8, 16, and 24. The change from baseline to the other study time points will indicate the treatment effect with resveratrol and sirolimus.

Initially, by using the paired t-test we will test whether these effects are statistically significant. Multivariate linear regression models will be used to assess the relationship between serum VEGF-D change and the covariates including patient's clinical or demographic factors. Linear mixed models will be performed to detect the correlation between serum VEGF-D and the covariates taking into account the correlation between repeated measurements within the same patient. A repeated measures ANOVA model and linear mixed models will be performed to compare the serum VEGF-D at follow-up visits to the baseline taking into account the correlation between repeated measurements within the same patient.

**Specific Aim #2:** To determine the safety and adverse effect profile of combined resveratrol and sirolimus in LAM. Subjects will be evaluable for safety if they have received at least one dose of the study drug. The frequency, severity and duration of all adverse events, regardless of cause, will be recorded on the case report forms. The frequency and severity of adverse events will be calculated by patient, with each patient counted once using the most severe grade experienced. The duration of adverse events

will be calculated by the number of days each event persisted. Adverse events will be tabulated by body system and by severity using the NCI Common Terminology Criteria for Adverse Events (CTCAE) v4.0, which can be obtained from the CTEP website: <http://ctep.cancer.gov/reporting/ctc.html>. Tables will be generated for all adverse events including those that are judged to be possibly, probably or definitely related to the drug. In order to assess the safety and adverse effect profile of resveratrol in LAM, we will assign a binary indicator variable to indicate a patient with or without adverse events. A multivariable logistic regression model will be used to assess of the effect of the covariates on the probability of having adverse events for patient with LAM. All interested factors will be adjusted in the logistic regression model. Model selection will be based on stepwise criterion when appropriate.

**Specific Aim #3:** To determine the effect of combined resveratrol and sirolimus on lung function and quality of life parameters in patients with LAM. Lung function parameters (FEV1 and FVC) will be measured at the baseline visit, and at every in-person visit. DLCO will be measured at the baseline visit and the last study visit. Similar analysis plan as VEGF-D will be employed for the lung function parameters. We will use the following questionnaire-based assessments to determine the quality of life in this trial: St. George's Respiratory Questionnaire (SGRQ), EuroQOL scale, San Diego Shortness of Breath scale (SD-SOB), and A Tool to Assess Quality of Life in LAM (ATAQ-LAM). Written permission has been obtained to use all these questionnaires. The scores on each of these questionnaires will be calculated at baseline, and at every in-person visit. We will compare median values at baseline and 24 weeks with the Wilcoxon signed rank test for each of these scales.

**Home spirometry evaluation:** The spirometry values will be expressed as mean  $\pm$  SD. All spirometry maneuvers will be checked for acceptability and reproducibility as specified in the ATS/ERS criteria (38) by an expert pulmonary physiologist. The spirometry values obtained from maneuvers that do not satisfy the ATS/ERS criteria for acceptability will not be used in the primary analysis. If spirometric values meet the acceptability criteria but fail to satisfy the repeatability criteria, those values will be graded for quality, but will be used in the primary analysis. Overall compliance with weekly home spirometry will be recorded and reported as a percentage. Comparison of home spirometry and office-based spirometry values will be performed using the Bland-Altman method at baseline, and at each time frame that patients get an office-based spirometry (i.e. every 8 weeks). Rate of change of FEV1 (slope) over time will be calculated by using all available values (without imputations) in a linear mixed effects model after considering the correlation of the observations within each subject, and the time between measurements will be treated as a fixed effect. In order to analyze if the trends obtained from short-term follow up with frequent home spirometry correlate with overall disease trajectory, we will compare the rate of decline obtained after 8 weeks of home spirometry to the overall rate of decline obtained after 24 weeks of follow up. A similar analysis plan will be employed for serum VEGF-D, and other biomarkers. All statistical analyses for this study will be performed using SAS, version 9.4 (SAS Institute Cary NC).

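### The stated 80% power does not follow from an SD of 800 for the paired difference: 20 pairs give about 61%, and 80% fits only if 800 is the per-visit SD

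*Combined protocol and SAP*

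**What the plan says.** The sample-size paragraph in Section 15 (Statistical considerations), repeated in the synopsis under Sample Size, builds the target in these steps:

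- Patients are already on sirolimus, so the plan expects that "the starting serum VEGF-D level in our study will be approximately 1,000pg/ml". A 42% change from that level is 420 pg/ml.
- The power claim reads "Assuming the correlation between the baseline and subsequent VEGF-D levels is 0.7, a sample size of 20 subjects will provide 80% power", and the aim is "to detect a mean VEGF-D difference from baseline to post-treatment of 420pg/ml or higher".
- The remaining inputs are given as "with the level of significant of 0.05 and a standard deviation of 800 for the difference".
- A 20% dropout allowance then takes 20 evaluable subjects to 25 enrolled.

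For the primary analysis, Section 15 says "Paired t-test will be performed to detect the difference of serum VEGF-D after 24 weeks of treatment", compared with the value before enrolment. The significance rule is "A p-value less than 0.05 will be considered as statistically significant". Neither place says whether the test is one-sided or two-sided, or where the 800 comes from.

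**The concern.** The power of a paired t-test depends on the mean difference, the SD of the difference, the number of pairs and alpha. The SD of the difference can be given directly, or derived from the SD at each visit together with the correlation between visits. The plan gives a correlation and also an SD that it says already belongs to the difference. If that label is right, the correlation is redundant and the power must follow from 800 alone, which it does not. If the correlation was used, the 800 must be the SD at a single visit and the label is wrong.

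This paragraph is the only justification for 20 evaluable and 25 enrolled patients. If the label is right, a non-significant result would be read as coming from a test with 80% power when the power was about 61%. If the label is wrong, anyone who takes 800 as the paired SD for later planning uses a variance of 640,000 instead of 384,000, which is two-thirds too large (640,000 / 384,000 = 1.67).

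**Working it through.** **Inputs, all from Section 15:** difference 420 pg/ml; n = 20 pairs; alpha 0.05; SD 800 pg/ml; correlation r = 0.7; dropout 20%. Two-sided testing is an assumption, so one-sided results are shown as well.

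**Method.** Power comes from the noncentral t distribution with n − 1 = 19 degrees of freedom and noncentrality difference × √n / SD of the difference.

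**Reading A: 800 is the SD of the difference, as written.**

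- Standardised difference: 420 / 800 = 0.525.
- Noncentrality: 0.525 × √20 = 2.35.
- Two-sided power: **60.6%** (simulation: 60.7%).

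**Reading B: 800 is the SD at each visit, equal at both visits, with r = 0.7.**

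- SD of the difference: 800 × √(2 × (1 − 0.7)) = 800 × √0.6 = 619.7 pg/ml.
- Standardised difference: 420 / 619.7 = 0.678.
- Noncentrality: 0.678 × √20 = 3.03.
- Two-sided power: **82.0%** (simulation: 82.0%). With n = 19 it is 79.8%, so 20 is the smallest n that reaches 80%.

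Reading B therefore reproduces the plan's n exactly. The enrolment figure also reproduces: 20 / (1 − 0.2) = 25.

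**Can another convention rescue Reading A?**

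| SD of difference 800 | n = 20 | n = 25 |
|---|---|---|
| Two-sided t | 60.6% | 71.2% |
| One-sided t | 73.2% | 81.7% |
| Two-sided normal approximation | 65.1% | not run |
| One-sided normal approximation | 75.9% | not run |

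Only a one-sided test with all 25 enrolled patients passes 80%. The plan attaches 80% to 20 subjects and adds dropout afterwards, so that is not the calculation it describes. A one-sided test under Reading B does not match either: it gives 89.9% at n = 20 and would need only 15 pairs for 80%.

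**What each reading implies (two-sided, 80% power).**

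| | Reading A | Reading B |
|---|---|---|
| Pairs needed for 420 pg/ml | 31 (30 gives 79.4%, 31 gives 80.7%) | 20 |
| Enrolled at 20% dropout | 31 / 0.8 = 38.75, so 39 | 25 |
| Detectable difference with 20 pairs | 528 pg/ml (53% of 1,000) | 409 pg/ml |

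With 20 pairs, any SD of the difference up to about 636 pg/ml gives 80% power for 420 pg/ml. If 800 were the SD of the difference and r were also 0.7, the SD at each visit would be 800 / √0.6 = 1,033 pg/ml, about as large as the assumed mean.

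**The case against.** The strongest reply is that this is a labelling slip and the design is sound. The correlation is useful only under Reading B, and Reading B returns n = 20 exactly. On that view the power, the 20 evaluable and the 25 enrolled all stand, and the 61% describes a calculation nobody made. This is probably what happened. It does not make the sentence correct, because the documents never say which figure is mislabelled, and a reader who takes the words as they stand gets 61%.

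A second argument is that an SD of change of 800 pg/ml is implausible. Section 15 puts the largest serial change in the MILES placebo group at 42%, about 420 pg/ml at the assumed starting level, and Section 5.2 (criterion 5) admits only patients whose two on-sirolimus values vary by 15% or less. The point has some force, but treatment response and patients with high baselines add spread. It also tells against 620 pg/ml, which likewise exceeds 420, so it does not choose between the readings. What it does show is that the 800 needs a source.

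Third, Section 14 calls the study exploratory, it will supply its own SD for later planning, and an overstated paired SD would enlarge a later trial rather than underpower it. All of that is fair and limits the harm to phase III planning. The plan still makes an explicit power claim for its primary test at the 0.05 level.

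**Conclusion.** The concern holds. As written, the inputs give 60.6% two-sided power (73.2% one-sided), not 80%. Among the standard readings of the stated inputs at n = 20, only the one that treats 800 as the per-visit SD with a correlation of 0.7 and a two-sided test gives the stated figure (82.0%, with n = 20 reproduced exactly). The label on the SD is the more likely error, in which case the sample size stands. If the label is right, the chance of missing a true change of 420 pg/ml is about 39%, nearly double the stated 20%.

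These results assume normally distributed differences and, for Reading B, the same SD at both visits. The two-sided test is also an assumption, because the plan does not state the side.

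**What to change.** The sponsor should establish from the original calculation which SD the 800 is, and then correct Section 15 and the synopsis together. The corrected text should give the source of the SD and the sidedness of the test. The wording depends on the answer:

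- **If 800 is the per-visit SD:** state an SD of 800 pg/ml at each visit and a correlation of 0.7, giving an SD of the paired difference of about 620 pg/ml; 20 evaluable subjects then give 82% power for a mean change of 420 pg/ml at two-sided alpha 0.05.
- **If 800 is the SD of the paired difference:** remove the correlation and state that 20 evaluable subjects give 61% power for 420 pg/ml at two-sided alpha 0.05, with 80% power only for about 530 pg/ml. The sponsor would then be knowingly accepting that power; keeping 80% for 420 pg/ml would instead take 31 evaluable and 39 enrolled.

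The cost is one sentence in two places. Neither restatement adds patients, visits or procedures. Under the second, the stated power becomes less favourable.
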